1.2.2. Study Rationale

The initial development activities for tafamidis were undertaken in patients with TTR-FAP. Safety data in this population, and the results from the TRACS study, led to the initiation of Protocol Fx1B-201, a 12-month trial of tafamidis in patients with TTR-CM. The results of the Fx1B-201 study will be used in the design of a Phase 3 program that will evaluate the efficacy and safety of tafamidis in TTR-CM.

TTR-CM is a slowly progressing disease with a median survival of approximately 60 months [14, 15]. It is currently not known whether tafamidis will be effective in slowing or halting the progression of TTR amyloid cardiomyopathy, or when such an impact would become evident. Therefore, the purpose of the current study is to assess the long-term safety and

efficacy of tafamidis in patients with ATTR-CM. Eligible patients who successfully completed Protocol Fx1B-201, having received open-label tafamidis for 12 months, may enroll in Protocol Fx1B-303 and continue to receive open-label tafamidis for up to an additional 10 years.

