9.2.8. Mortality and Hospitalization

The endpoints of mortality and hospitalization (all cause and cardiac-related) will be analyzed individually and as composite measures.

A Kaplan-Meier plot of time to event from the start of Protocol Fx1B-201 will be generated, and the event rate and associated 95% confidence intervals will be presented at 1, 2, 3, and 4 years since the start of the investigational drug.

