## **5. ANALYSIS SETS**

### **5.1. Safety Analysis Population**

The safety analysis population consists of all subjects who are enrolled in this study and who have taken at least one dose of study medication.

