#### 8.1.3. Analyses for Time to Event Endpoints

Kaplan-Meier estimates will be computed for all time to event endpoints, including median and interquartile ranges, where appropriate. 95% confidence intervals will be presented at yearly intervals from the start of the investigational drug (baseline of Fx1B-201). Time to event will use randomization and onset of disease as starting points for the calculation of time to event.

Subjects are required to survive to enroll in the parent study (Fx1B-201). Such conditions yield a left-truncated death time distribution from symptom onset. To account for the potential immortal time bias, the time to death from onset of symptom will be analyzed using the delayed entry (left truncation) technique. Survival probabilities will be calculated conditional on subjects having survived until study entry of the parent study (Fx1B-201). SAS codes for the delayed entry (left truncation) technique are provided in Appendix 5.

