## 8.3. Safety Analyses

Safety data will be summarized for the safety analysis population.

**Treatment and Disposition of Subjects:** Subject evaluation groups will show end of study subject disposition and will show which subjects were analyzed for efficacy, as well as for

safety (adverse events and laboratory data). Frequency counts will be supplied for subject discontinuation(s) by treatment.

A listing of treatment duration for each subject will be reported in accordance with the sponsor reporting standards.

**Demographic and Baseline Characteristics.** A break-down of demographic data will be provided for age, race, weight, body mass index, and height. Each will be summarized by sex at birth and ‘All Subjects’ in accordance with the sponsor reporting standards. All baseline and disease characteristics will also be summarized for Fx1B-201 and B3461026, respectively.

**Discontinuations.** Subject discontinuations or temporary discontinuations due to adverse events will be detailed and summarized.

**Adverse events (AEs):** Adverse events will be summarized by causality and severity.

**Mortality and Hospitalization (all-cause and cardiac-related):** Time to all-cause mortality and time to cardiac-related mortality will be calculated from the first dose of the randomized treatment in Study Fx1B-201, and from onset of symptom, respectively. For cardiac-related mortality, subjects who died for reasons other than cardiovascular will be designated as censored at the time of death. Subjects alive at the end of the study will be censored at the last visit date. Death after discontinuation will be censored at time of discontinuation. For subjects who have received a liver and/or heart transplant, time will be censored at the time of transplant. The analyses will use the methods described for time to event endpoints in [Section 8.1.3](#). The analyses will be performed on the safety analysis population (defined in [Section 5.1](#)).

The number and percentage of subjects hospitalized (all-cause and cardiac-related) during the study will be summarized descriptively.

**Hematology, Biochemistry and Urinalysis:** Descriptive statistics will be provided for each test result and for change from baseline by visit.

Baseline is defined as the last evaluation prior to the first dose of study drug in Study Fx1B-201.

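### The cardiac-death Kaplan-Meier censors non-cardiac deaths and is presented as an event rate, so it overstates the probability of cardiac death; no cumulative incidence is planned (minor)

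*SAP*

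**What the plan says.** On the handling of other deaths, SAP 8.3 states: "For cardiac-related mortality, subjects who died for reasons other than cardiovascular will be designated as censored at the time of death". It sends the analysis to SAP 8.1.3, where "Kaplan-Meier estimates will be computed for all time to event endpoints", with confidence intervals at yearly times counted from the start of drug in the parent study.

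Protocol 9.2.8 covers all-cause and cardiac-related events. It plans a Kaplan-Meier plot and says that "the event rate and associated 95% confidence intervals will be presented at 1, 2, 3, and 4 years". The SAP itself does not use the event-rate label.

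On the time origin, SAP 8.3 counts all-cause and cardiac-related mortality "from the first dose of the randomized treatment in Study Fx1B-201, and from onset of symptom, respectively". Read literally, this puts cardiac mortality on the symptom-onset scale only, whereas SAP 8.1.3 names both origins. For the symptom-onset scale, SAP 8.1.3 adds that "the time to death from onset of symptom will be analyzed using the delayed entry (left truncation) technique". The code in Appendix 4 (cited in 8.1.3 as Appendix 5) lets subjects enter at the start of the parent study. It is a product-limit estimate with a single death flag, so it does not yield a cumulative incidence.

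The mortality analyses use the safety population: "all subjects who are enrolled in this study and who have taken at least one dose of study medication". Protocol 1.2.2 explains who can be in it: "Eligible patients who successfully completed Protocol Fx1B-201, having received open-label tafamidis for 12 months, may enroll in Protocol Fx1B-303".

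**The concern.** A subject who dies of a non-cardiac cause can no longer die a cardiac death. Kaplan-Meier with that death censored treats the subject as still able to, and spreads the subject's weight over those remaining at risk. The result is a valid summary of the cause-specific hazard. One minus the curve is not the probability of cardiac death, and it exceeds that probability as soon as a non-cardiac death precedes a cardiac one.

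A reader who sees an event rate with a confidence interval at year 4 will take it as the proportion expected to die a cardiac death by then. SAP 3.2 foresees presentation at scientific meetings, publication and regulatory use, so the label matters even though the study tests no hypothesis.

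**Working it through.** The documents state no expected cardiac-death probability, so there is no planned figure to reproduce. The size is illustrated with constant hazards.

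**Inputs**
- Total death hazard, main case: Protocol 1.2.2 gives "a median survival of approximately 60 months", so λ = ln 2 / 5 = 0.1386 per year.
- Total death hazard, low case: 2 of 35 died in the 12-month parent study (Protocol 1.2.4), so λ = −ln(1 − 2/35) = 0.0588 per year.
- Cardiac share of deaths p: 42% in Protocol 1.2, read here as a share of deaths (an assumption). The definition in SAP 6.2 is broad: the whole cardiac disorders class plus stroke terms, death and disease progression. The range is therefore carried up to 90%.
- Years at risk T: time counts from parent-study first dose, but everyone analysed survived that 12-month study. Year 4 therefore has T = 3, and year 10 has T = 9.

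**Formulas**
- One minus Kaplan-Meier, non-cardiac deaths censored: 1 − exp(−pλT)
- Cumulative incidence of cardiac death: p × [1 − exp(−λT)]

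Example, year 4, 60-month median, p = 0.42: 1 − exp(−0.42 × 0.1386 × 3) = 16.0%, against 0.42 × [1 − exp(−0.1386 × 3)] = 0.42 × 0.340 = 14.3%.

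| Hazard | Cardiac share | Year | 1 − KM | Cumulative incidence | Excess (points) |
|---|---|---|---|---|---|
| 60-month median | 42% | 4 | 16.0% | 14.3% | 1.7 |
| 60-month median | 70% | 4 | 25.3% | 23.8% | 1.4 |
| 60-month median | 90% | 4 | 31.2% | 30.6% | 0.6 |
| 60-month median | 42% | 10 | 40.8% | 29.9% | 10.9 |
| 60-month median | 70% | 10 | 58.2% | 49.9% | 8.3 |
| 60-month median | 90% | 10 | 67.5% | 64.2% | 3.3 |
| Parent study | 42% | 4 | 7.1% | 6.8% | 0.35 |
| Parent study | 90% | 4 | 14.7% | 14.6% | 0.13 |

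(Excesses are taken before rounding.)

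**Precision.** At most 35 − 2 = 33 subjects can be in the safety population. With four-year survival exp(−3 × 0.1386) = 66.0%, the sampling standard deviation is √(0.66 × 0.34 / 33) = 8.2 points. At a 90% cardiac share, the expected number of non-cardiac deaths by year 4 is 33 × 0.10 × 0.34 = 1.1.

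**Risk sets on the symptom-onset scale.** Protocol 1.2.4 gives a disease duration of about 8 years at parent-study entry but no spread, so the spread is assumed. The setup was simulated with two million subjects: entry times normal with mean 8 years and at least 0.5 years, no deaths in the first year after entry, then λ = 0.1386, with 42% of deaths cardiac. At year 12 from onset:

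| Entry SD (years) | 1 − KM, entry at parent-study start | Aalen-Johansen, entry at parent-study start | Aalen-Johansen, entry at Fx1B-303 enrolment |
|---|---|---|---|
| 2 | 25.6% | 21.4% | 35.4% |
| 4 | 32.7% | 25.6% | 32.0% |

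In this setup the hazard is constant from 1.5 years after onset (0.5 plus the death-free year). Given survival to that point, the target is therefore 0.42 × [1 − exp(−0.1386 × 10.5)] = 32.2%. The 35.4% scatters around it because very few subjects are at risk soon after onset. Entry at parent-study start counts a death-free year as time at risk and pulls the estimate down. Changing the estimator while keeping the Appendix 4 entry time would therefore not give the probability of cardiac death.

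**The case against.** The best case for leaving the plan alone is this. Censoring other causes is the standard cause-specific analysis. The study is descriptive (SAP 4.1), and all-cause mortality, where non-cardiac deaths count as events, is reported beside it. The event-rate wording is the protocol's and is attached to time from drug start; the SAP speaks of Kaplan-Meier estimates and survival probabilities, and Protocol 9 allows the SAP to modify the plan. Under the SAP's broad cardiac definition the year-4 excess is well under one point, far below sampling error.

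Most of this stands, and it makes the point minor. It does not remove it. The bias has a fixed direction that more subjects would not cure, SAP 8.1.3 sets no upper limit on the yearly reporting times, and nothing in the SAP tells the reader that the curve is not a probability of cardiac death.

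Three stronger readings are tempting, and the documents do not support them.
- A reader might take four full years at risk by year 4, which gives 20.8% against 17.9%, or 2.9 points. The first year is death-free by the way the safety population is formed.
- A reader might use the natural-history rate in Protocol 1.2, 0.03 deaths per patient-month, which at a 42% cardiac share gives 36.5% against 27.7% at year 4. That cohort was not on tafamidis, and the parent study's own mortality was far lower.
- A reader might infer that all-cause survival is also biased, because SAP 8.3 censors deaths after discontinuation at discontinuation. That rule fits the on-study definition of death in SAP 6.2 and causes no bias if withdrawal is unrelated to prognosis. The documents give no withdrawal rates or later death rates from which to claim otherwise.

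**Conclusion.** The point holds as a minor matter of estimation and labelling, confined to cardiac-related mortality. As planned, the event rate overstates the probability of cardiac death. Through year 4 from first dose the overstatement is 0.6 to 1.7 points with a 60-month median and 0.35 points or less at the parent-study hazard, against a sampling standard deviation of about 8 points. By year 10 it is 3.3 to 10.9 points with the 60-month median.

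These sizes rest on constant hazards, on reading the 42% as a share of deaths, on applying the background median to this cohort, and on a death-free first year. The direction rests on none of them. It does not follow that censoring non-cardiac deaths is invalid or that the mortality results as a whole are unreliable: the cause-specific analysis is legitimate under its own name.

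**What to change.** In SAP 8.1.3 and 8.3:

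1. Report cardiac death as an Aalen-Johansen cumulative incidence with 95% confidence intervals at the yearly times, with non-cardiac death as a competing event. On the symptom-onset scale, let subjects enter the risk set at Fx1B-303 enrolment, not at parent-study start as in Appendix 4. On the drug-start scale, use the same entry point and state that the estimate is conditional on surviving the parent study.
2. Keep Kaplan-Meier for all-cause death.
3. If the Kaplan-Meier curve with non-cardiac deaths censored is kept, label it cause-specific and do not call it an event rate.
4. As a wording clarification, state which time origin or origins apply to cardiac mortality.

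The cost is SAP wording and one cumulative-incidence routine that accepts entry times. No new data are needed.

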Data on 29 patients (mean age 74 years) have been analyzed (18 wild-type and 11 V122I). Most patients are male (92%) and are New York Heart Association (NYHA) Classification I or II with significant cardiac symptoms reported at baseline. After an average follow-up time of 16 months, 11 patients died and one patient underwent cardiac transplant, giving the proportion of death/cardiac death of 41%, and a death rate per patient month exposure of 0.03. In addition, 41% of the patients experienced a cardiac hospitalization at least once, and 55% of the patients died or had a cardiac hospitalization. Preliminary analysis of cardiac assessments demonstrate significantly elevated NT-Pro-BNP and troponin levels, abnormal functional status as assessed by the 6-minute walk test, and significant diastolic dysfunction and thickened ventricles as assessed by echocardiography and cardiac MRI.

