6.3. Subject Withdrawal

Subjects may withdraw from the study at any time at their own request, or they may be withdrawn at any time at the discretion of the investigator or sponsor for safety or behavioral reasons, or the inability of the subject to comply with the protocol required schedule of study visits or procedures at a given study site. In addition, the Sponsor may choose to discontinue this study, at which time all subjects will be withdrawn.

A subject may be withdrawn from the study for any of the following reasons:

- Withdrawal of consent;
- Adverse event;
- Protocol noncompliance;
- Subject lost to follow-up;
- Subject death.

Subjects who are prematurely withdrawn from the study will not be replaced. Subjects who discontinue from the study at any time following enrollment will have a final end of study visit performed, including all safety and efficacy assessments, at the time of discontinuation.

Upon regulatory approval of tafamidis for the treatment of TTR-CM in their respective country, and access to prescription tafamidis, subjects may be withdrawn from the study. The decision to withdraw subjects in a country will be done in consultation between the investigator and the sponsor. Subjects will have all end of study procedures completed prior to study withdrawal. These subjects are considered completers.

If a subject does not return for a scheduled visit, every effort should be made to contact the subject. In any circumstance, every effort should be made to document subject outcome, if possible. The investigator should inquire about the reason for withdrawal, request the subject to return all unused investigational product(s), request the subject to return for a final visit, if applicable, and follow-up with the subject regarding any unresolved adverse events (AEs).

If the subject withdraws from the study, and also withdraws consent for disclosure of future information, no further evaluations should be performed, and no additional data should be collected. The sponsor may retain and continue to use any data collected before such withdrawal of consent.

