8.2. Reporting Period

For SAEs, the active reporting period to Pfizer or its designated representative begins from the time that the subject provides informed consent, which is obtained prior to the subject's participation in the study, ie, prior to undergoing any study-related procedure and/or receiving investigational product, through and including 28 calendar days after the last administration of the investigational product. Should an investigator be made aware of any SAE occurring any time after the active reporting period, it must be promptly reported.

- AEs (serious and non-serious) should be recorded on the CRF from the time the subject has taken at least one dose of study treatment through last subject visit.

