**8. Mortality and hospitalization (all-cause and cardiac-related)**

All-cause of mortality is defined as any death occurring during the study. Cardiac-related mortality will be any mortality meeting the following MedDRA criterion: 1) AE body system (AEBODSYS) = "CARDIAC DISORDERS", or 2) AE preferred term (AEDECOD) in (CHEST DISCOMFORT, CHEST PAIN, DEATH, CEREBROVASCULAR ACCIDENT, EMBOLIC STROKE, DISEASE

PROGRESSION). Description on the time to mortality analysis can be found in [Section 8.1.3](#).

All cause of hospitalization is defined as any adverse event for which SAE type “3=Hospitalization” in the Adverse Event (AE) CRF. The cardiac-related hospitalization will be any hospitalization meeting the following MedDRA criterion:1) AE body system (AEBODSYS) = “CARDIAC DISORDERS”, or 2) AE preferred term (AEDECOD ) in (CHEST DISCOMFORT, CHEST PAIN, DEATH, CEREBROVASCULAR ACCIDENT, EMBOLIC STROKE, DISEASE PROGRESSION).

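### SAP 8.3 censors every death after discontinuation and plans no sensitivity analysis; if worsening subjects leave shortly before death, survival is likely overstated

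*SAP*

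**What the plan says.** SAP 8.3 (Mortality and Hospitalization) sets the rules for time to all-cause and time to cardiac-related death, measured from first dose in Fx1B-201 and from symptom onset:

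- Deaths after exit: "Death after discontinuation will be censored at time of discontinuation".
- Survivors: "Subjects alive at the end of the study will be censored at the last visit date".
- Transplant: "For subjects who have received a liver and/or heart transplant, time will be censored at the time of transplant".

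SAP 6.2 item 8 matches this: "All-cause of mortality is defined as any death occurring during the study". SAP 8.1.3 names the estimator: "Kaplan-Meier estimates will be computed for all time to event endpoints". Confidence intervals are given at yearly points; protocol 9.2.8 names years 1 to 4.

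The SAP does not define discontinuation. In protocol 6.3 subjects discontinue from the study and have an end of study visit. Listed reasons include adverse events, withdrawn consent, noncompliance, loss to follow-up and death; inability to keep the visit schedule is also a ground. SAP 6.5 adds laboratory abnormalities and transplant. Subjects moving to prescription tafamidis count as completers.

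On what is known after exit, protocol 8.2 runs active SAE reporting "through and including 28 calendar days after the last administration of the investigational product" and requires later SAEs that come to the investigator's notice to be reported. Protocol 6.3 adds: "In any circumstance, every effort should be made to document subject outcome, if possible".

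**The concern.** Kaplan-Meier treats a censored subject as having the same future risk as those still under observation. That is doubtful when a subject with progressive cardiomyopathy leaves because of an adverse event or because visits have become impossible. Mean age was about 76 at Fx1B-201 enrolment, and the protocol puts median survival near 60 months (1.2.2), so health-related exits are to be expected.

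A subject who leaves the study and dies ten days after the last dose generates a reportable SAE, yet on the survival curve is event-free at exit. SAP 8.1.3 corrects for selection at the start of follow-up through delayed entry, but nothing examines selection at the end.

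Mortality is a listed endpoint, there is no control arm to share a bias, and SAP 3.2 foresees interim results for publication or regulatory use. The printed confidence intervals would not reflect this error.

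**Working it through.** The plan states no expected survival, number of deaths or power for this endpoint, so there is no figure of its own to reproduce.

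**Inputs**
- Median survival about 60 months (protocol 1.2.2): λ = ln 2 / 60 = 0.01155 per month.
- Alternative hazard from the natural-history cohort (TRACS): 0.03 per patient-month (protocol 1.2).
- Up to 35 subjects (protocol 9.1).
- f, the share of deaths that fall shortly after exit: **assumed**; not in the documents.

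**Step 1: no deaths lost.** S(48 months) = exp(−48λ) = exp(−0.5545) = 57.4%. With 0.03 per month, exp(−1.44) = 23.7%.

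**Step 2: present rule, failing subjects leave just before death.** A share f of deaths becomes censored with almost no loss of time at risk, so the estimated hazard is about (1−f)λ, S(48) = exp(−48λ(1−f)), and the median is 60/(1−f).

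| f (assumed) | 4-year survival, 60-month median | Apparent median, months | 4-year survival, 0.03/month |
|---|---|---|---|
| 0 | 57.4% | 60 | 23.7% |
| 10% | 60.7% | 67 | 27.4% |
| 20% | 64.2% | 75 | 31.6% |
| 30% | 67.8% | 86 | 36.5% |

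Simulations with lead times of 0 to 1 and 0.5 to 6 months between exit and death agree within about 1.1 points. With 35 subjects and f = 20% under the 60-month median, the mean overstatement is 6.3 points (95% of simulated trials between 0 and 14.5).

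**Step 3: other reasons for leaving.** Simulated at 1% exit per month, 60-month anchor:
- Exit unrelated to prognosis: 57.4% against a true 57.5%, so no bias.
- Two equal groups with hazards 0.5λ and 1.5λ, lower-risk group leaves: 57.6% against 59.5%, 1.9 points too low.
- Same groups, higher-risk group leaves: 61.5% against 59.7%, 1.8 points too high.

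**Step 4: test of the remedy.** Suppose exit is unrelated to prognosis, deaths up to 12 months after exit are counted because they happen to be known, and everyone else is still censored at exit. Survival is then 54.3% against a true 57.5%: biased downward. With a 1-month window the figures are 56.9% and 57.2%. Censoring survivors at the end of the window instead of at exit removes the error (57.4% against 57.4%).

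**Step 5: what 28 days recovers.** If exit coincides with the last dose and lead times are spread evenly over 3 months (assumed), about 28/91 = 31% of the lost deaths fall in the window. For f = 20%, the share still lost is 20% × 0.69 = 13.8%, and S(48) = exp(−0.5545 × 0.862) = 62.0%, compared with 64.2% in Step 2 and 57.4% true. The window helps but does not close the gap, so a second curve is needed.

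**The case against.** The rule is prespecified and matches the SAP's on-study definition of mortality. The study is descriptive, with no hypotheses (SAP 4.1), and reasons for discontinuation will be tabulated (SAP 6.5). At 57.4% survival with 35 subjects and complete follow-up, the approximate 95% half-width is 1.96 × √(0.574 × 0.426 / 35) = 16 points, wider than the illustrated 3 to 10 points. All of this stands and lowers the severity. It does not make the assumption tested: a wide interval expresses chance, not a shift in one direction.

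A reader might infer three stronger things that the documents do not support.

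- **That follow-up ends when treatment stops.** The SAP says discontinuation, without treatment, and protocol 6.3 uses the word for leaving the study. A subject who stops capsules but dies before leaving may well be an on-study death and an event. Subjects also contribute to the curve until they are censored.
- **That survival is certainly overstated.** The documents give no numbers or reasons for withdrawals, and Step 3 shows cases with no bias or the opposite bias.
- **That censoring transplants spoils a planned comparison with TRACS.** The protocol reports that "11 patients died and one patient underwent cardiac transplant, giving the proportion of death/cardiac death of 41" per cent; 12/29 = 41.4%, while deaths alone give 11/29 = 37.9%, so the transplant appears to be included. But neither document plans to set this study's survival beside that figure, and the protocol's 12-month comparison for Fx1B-201 reports deaths.

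An unrestricted rule to count every known death is also open to challenge. Outcome is documented only where possible, and collection stops if consent for disclosure is withdrawn (protocol 6.3). Step 4 shows the result of counting deaths selectively.

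**Conclusion.** The concern holds in conditional form. SAP 8.3 removes every death after discontinuation as an event, including deaths that the protocol requires to be reported, under an undefined term and without a sensitivity analysis. Overstated survival is the likely direction, given an elderly population and health-related grounds for leaving, but it is not a certainty.

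Under a constant hazard with a 60-month median, the overstatement at 4 years would be about 3, 7 or 10 points for an assumed 10, 20 or 30% of deaths just after exit. These figures show scale and are not estimates for this study. The 60-month median has no stated time origin, while the main curve starts at first dose in Fx1B-201.

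Severity: should be fixed.

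**What to change.** In SAP 8.3, with SAP 6.2 item 8 aligned:

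1. **Define discontinuation**, stating whether its date is last dose or study exit, and confirm that deaths before study exit remain events.
2. **Main curve:** count as an event, at its date, every death through 28 days after the last dose. Protocol 8.2 already requires SAE reporting for all subjects in that period. Censor survivors at the end of the window, or at the last date known alive if earlier; at transition for those moving to prescription supply; and at withdrawal of consent for disclosure where that occurs.
3. **Sensitivity curve, all known deaths:** seek vital status for every withdrawn subject where consent allows, count all deaths, and censor the others at the date last known alive. Without systematic ascertainment this curve is biased downward.
4. **Keep the present on-study curve** as a sensitivity analysis, and tabulate reasons for censoring and known deaths after discontinuation.

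A death-or-transplant curve is optional, needed only if results are set beside the 41% TRACS figure.

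The cost is SAP wording, extra curves and a vital-status check. Protocol 8.2 records AEs on the CRF only to the last subject visit, and SAP 6.2 classifies cardiac deaths from coded AE terms, so later deaths must be reconciled with the safety reports. A few off-drug deaths will enter the main curve, and survival may look slightly less favourable.
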